2.4 Rationale for choice of combination drugs

The rationale to combine alpelisib with fulvestrant is based on the following:

- The demonstrated efficacy of fulvestrant in this patient population ([Section 1.2.1](#))
- Synergism between PI3K inhibition with alpelisib and the effect of fulvestrant seen in preclinical experiments the combination being significantly more effective than each drug taken separately ([Section 1.2.3](#))
- No drug-drug interaction between alpelisib and fulvestrant and same pharmacokinetic results for alpelisib in the combination with fulvestrant compared to single agent alpelisib [[CBYL719X2101 study](#)] ([Section 1.2.4.2](#))
- Preliminary preclinical and clinical data suggesting acceptable safety profile of the combination [[CBYL719X2101 study](#)] ([Section 1.2.3.3](#))
- Preliminary promising clinical activity [[CBYL719X2101 study](#)].

2.5 Rationale for choice of comparators drugs

Patients enrolled in the study will either be in first line or in second line for the treatment of their metastatic disease.

In first line setting, currently approved treatment options include tamoxifen, AI or palbociclib in combination with letrozole.

The recently presented data from the FIRST study, conducted in HR+ HER2-negative advanced breast cancer patients with no prior endocrine therapy or with long DFS after adjuvant endocrine therapy, showed superiority of fulvestrant 500 mg compared to anastrozole ([Robertson 2014](#)). Despite methodological limitations linked to indirect comparisons, the benefit brought by fulvestrant over anastrozole appears to be of the same extent than the one brought by the addition of palbociclib to letrozole. FALCON (ClinicalTrials.gov identifier: NCT01602380), a randomized phase III study comparing fulvestrant 500 mg with anastrozole as first-line treatment for postmenopausal women with HR+ MBC, completed enrollment in September 2014; results are still pending.

Taken together, these data support fulvestrant 500 mg as an acceptable therapy in the first-line metastatic setting.

In second line setting, several acceptable options are available ([NCCN 2.2015](#)) and include Fulvestrant. In addition, Fulvestrant is currently approved for the treatment of HR+ metastatic breast cancer in postmenopausal women with disease progression following anti-estrogen therapy. Hence, fulvestrant is considered a standard therapy for patients who have progressed on or after treatment with other endocrine agents and who require a well-tolerated alternative therapy ([Ciruelos et al 2014](#)).

In conclusion, fulvestrant at the selected dose of 500 mg given intramuscularly at one month intervals, with an additional 500 mg dose given 2 weeks after the initial dose, is considered an appropriate comparator arm for this study (see also [Section 1.2.1](#)).

2.6 Risks and benefits

2.6.1 Potential benefit for participants

Treatment with alpelisib in combination with fulvestrant may result in an improved clinical benefit compared to fulvestrant alone in men and postmenopausal women with HR+, HER2-

negative advanced breast cancer, which progressed on or after AI treatment. All patients enrolled in this trial will receive an active endocrine therapy for their disease (see [Section 2.5](#)). Based on preclinical and preliminary clinical data (see [Section 1.2.3](#)), treatment with alpelisib in combination with fulvestrant is expected to be well tolerated and it is hypothesized that it will result in delayed disease progression by inhibiting proliferation of endocrine-resistant breast cancer cells.

For further details on clinical safety, please refer to [Section 1.2.2](#) and the latest version of [Alpelisib (BYL719) Investigators Brochure].

2.6.2 Potential risks to clinical trial participants

Patients in this study will be carefully monitored for key toxicities that have been observed with alpelisib (see [Section 1.2.2](#)), fulvestrant (see [Section 1.2.1](#)) or the combination of both (see [Section 1.2.3](#)) with the following assessments (see [Section 7](#)): periodic laboratory, renal and liver function, urinalysis and ECG.

Risk will be further minimized by adherence to inclusion/exclusion selection criteria (see [Section 5](#)), avoidance of prohibited medication (see [Section 6.4.3](#)), close safety monitoring (see [Section 8](#)) and dose adjustment guidelines (see [Section 6.3](#) and current fulvestrant prescribing information [Faslodex® prescribing information]. PK sampling will be conducted in patients to assess plasma concentration of the study drug to evaluate any potential drug interaction. An independent data monitoring committee (DMC) (see [Section 8.6](#)) will be constituted and will monitor safety, efficacy and available PK data as outlined in the protocol. A Steering Committee (SC) (see [Section 8.7](#)) will be established comprising of investigators and Novartis personnel participating in the trial to ensure transparent management of the trial according to the protocol. A Novartis Safety Management Team (SMT) periodically reviews and evaluates all emerging data across the alpelisib program for potential safety signal assessment in a timely manner.

2.6.3 Risks related to study procedures

Study related risks include, but are not limited to collection of fresh tumor samples, blood collections, the different imaging methods incl. Echocardiogram (ECHO) or multiple gated acquisition (MUGA) scan, bone scans and electrocardiograms (ECGs). Please refer to the Consent Form for more information.

2.6.4 Risk management strategies

The risk to subjects in this trial will be minimized by compliance with the eligibility criteria and study procedures, close clinical monitoring, recommendations for concomitant medications, guidance for prohibited medications and dose adjustments as outlined in [Section 6.3](#). There may be unforeseen risks with alpelisib.

Based on key anticipated benefits and potential risks, the benefit-risk balance is anticipated to be positive for the target population of this trial.

3 Objectives and endpoints

Objectives and related selected endpoints are described in [Table 3-1](#) below. More details are described in [Section 10](#) as referred in the [Table 3-1](#).

[figure not shown]

Table 3-1 Objectives and related endpoints

Objective	Endpoint	Analysis
Primary		Refer to Section 10.4
• To determine whether treatment with alpelisib in combination with fulvestrant prolongs PFS compared to treatment with placebo in combination with fulvestrant for patients with PIK3CA mutant status	PFS based on local radiology assessments and using RECIST 1.1 criteria in the PIK3CA mutant cohort	
Key secondary		Refer to Section 10.5.1
To determine whether treatment with alpelisib in combination with fulvestrant prolongs overall survival (OS) compared to treatment with placebo in combination with fulvestrant for patients with PIK3CA mutant status	OS in the PIK3CA mutant cohort	
Other secondary		Refer to Section 10.5.2
• To establish proof of concept of treatment benefit with alpelisib in combination with fulvestrant with respect to PFS for patients with PIK3CA non-mutant status	PFS based on local radiology assessments and using RECIST 1.1 criteria in the PIK3CA non-mutant cohort	
• To evaluate the two treatment arms with respect to OS for patients with PIK3CA non-mutant status	OS in the PIK3CA non-mutant cohort	
• To evaluate the two treatment arms and cohorts of interest with respect to overall response rate (ORR), clinical benefit rate.	ORR and CBR in each of the PIK3CA mutant and non-mutant cohorts	
• To evaluate the two treatment arms and cohorts of interest with respect to time to deterioration of ECOG performance status.	Time to definitive deterioration of the ECOG performance status of the score from baseline in each of the PIK3CA mutant and non-mutant cohorts	
• To evaluate the safety and tolerability of alpelisib in combination with fulvestrant	
 • Type, frequency and severity of adverse events per CTCAEv4.03 • Type, frequency and severity of laboratory toxicities per CTCAEv4.03 	Refer to Section 10.5.3
• To evaluate change in global health status/QOL in the two treatment arms and cohorts of interest	
 • Time to 10% deterioration in the global health status/QOL scale score of the EORTC QLQ-C30 • Change from baseline in the global health status/QOL scale score of the EORTC QLQ-C30 in each of the PIK3CA mutant and non-mutant cohorts 	Refer to Section 10.5.4

4 Study design

4.1 Description of study design

This is a randomized, double blind, placebo controlled, international multi-center Phase III trial to determine the efficacy and safety of treatment with fulvestrant + alpelisib versus fulvestrant + placebo in men and postmenopausal women with HR+ HER2-negative advanced breast cancer which progressed on or after AI treatment.

PFS, as assessed by the local radiologists/investigators and using RECIST 1.1 criteria will be the primary endpoint. PFS as assessed through Blinded Independent Review Committee (BIRC) will be used for supportive evidence of the primary efficacy endpoint.

This study will consist of 4 phases: screening (35 days), randomized treatment, post-treatment disease progression follow-up, and post-treatment survival follow-up. Patients will be treated until disease progression, unacceptable toxicity, or discontinuation from the study treatment for any other reason.

In the randomized treatment phase, patients will be randomized 1:1 to receive:

- Control arm (Arm A): fulvestrant (500 mg intramuscular [as two 5 ml injections] on Day 1 and 15 of Cycle 1 and on Day 1 ± 3 days of every Cycle thereafter + Placebo (by mouth once daily, in a 28-day cycle)
OR
- Experimental arm (Arm B): fulvestrant (500 mg intramuscular [as two 5 ml injections] on Day 1 and 15 of Cycle 1 and on Day 1 ± 3 days of every Cycle thereafter + Alpelisib (300 mg by mouth once daily, in a 28-day cycle)

[figure not shown]
A total of approximately 560 patients will be enrolled; in which approximately 340 and 220 patients will be enrolled respectively to each of two cohorts: *PIK3CA* mutant and *PIK3CA* non-mutant. Within each of these two cohorts, randomization will be stratified by:

1. Lung and/or liver metastases (yes versus no)
2. Previous treatment with any CDK4/6 inhibitor (yes versus no)

The total number of patients pre-treated with any CDK4/6 inhibitor will be limited to 30% of the total number of patients.

One futility interim analysis is planned for the primary efficacy endpoint (PFS) in the *PIK3CA* mutant cohort at the expected time given in [Section 10.8](#). There is no intention to stop for superiority at this interim analysis. Another interim analysis that allows the study to stop for superior efficacy is planned in the *PIK3CA* mutant cohort, after all patients have been randomized and approximately 75% of the total PFS events have been documented, as per local assessments. If PFS is statistically significant, interim analyses for OS will also be conducted as detailed in [Section 10.5.1](#) and [Section 10.7](#).

Figure 4-1 Study design

An independent data monitoring committee (DMC) will be constituted and will monitor safety and efficacy as outlined in [Section 8.6](#) and [Section 10.7](#). A Study Steering Committee (SSC) will be established comprising investigators participating in the trial to ensure transparent management of the study according to the protocol through recommending and approving modifications as outlined in [Section 8.7](#).

Patients will receive treatment until disease progression, unacceptable toxicity, death, or discontinuation from the study treatment for any other reason. Patients will still be followed for efficacy when discontinuing study treatment for any reason other than disease progression or death. Patients will be followed for survival regardless of treatment discontinuation reason (except if consent is withdrawn or patient is lost to follow-up). Treatment crossover from placebo to alpelisib will not be permitted in this study.

This study will use an Interactive Response Technology (IRT) for patient screening, enrollment, randomization, discontinuation, stratification and alpelisib/placebo study medication management. In addition the IRT will manage the limitation of the number of patients with prior CDK4/6 inhibitors treatment up to 30% of the total number of the patients (see [Section 2.2](#)). If the study will continue in both cohorts to the final analyses, the maximum total number of CDK4/6 inhibitors pretreated patients will be 168.

4.1.1 Screening phase

At screening, the patient will provide a signed informed consent form prior to any study related activities. Signed informed consent will be obtained as early as Day-35. Collection and shipment of tumor sample (archived tissue or new biopsy) to Novartis designated laboratory should occur as soon as possible as early as Day-35 and no later than Day-21. The tumor sample will serve to establish the *PIK3CA* mutation status for randomization. It is recommended to wait for the central *PIK3CA* testing results before conducting other screening assessments. Additional screening evaluations must be performed within 28 days before treatment start; physical examinations and laboratory assessments will be performed within 14 days before treatment start (see [Section 7](#) for more details).

Patients will be screened in IRT only once patient has provided signed informed consent form.

4.1.2 Treatment phase

Patient eligibility will be checked once all screening procedures are completed. An eligibility review and confirmation will be embedded to the IRT system. Please refer to and comply with detailed guidelines in the IRT manual. Once the *PIK3CA* mutation status is identified by the Novartis designated laboratory, the IRT system will confirm the inclusion of eligible patients and randomize them in a 1:1 ratio to one of the two treatment groups described in [Section 4.1](#).

Sites will be kept blinded to *PIK3CA* mutation status provided by the Novartis designated laboratory.

In order to assess any potential impact of fulvestrant on the pharmacokinetics of alpelisib, sparse and trough PK samples for alpelisib and fulvestrant will be collected in approximately 200 patients from selected centers; trough PK samples will be collected for alpelisib and fulvestrant in all other patients as detailed in [Section 7.2.3](#).

Patients will receive treatment until disease progression (assessed by RECIST 1.1), unacceptable toxicity, death or discontinuation from treatment for any other reason. Efficacy and safety monitoring will continue as per visit schedule ([Table 7-1](#)).

All antineoplastic therapies given after the last dose of the study drug unless patient is lost to follow-up, or withdraws consent will be recorded in the electronic Case Report Forms (eCRFs).

4.1.3 Safety follow-up

After discontinuation of study treatment, all patients will be followed for safety, AEs and patient reported outcomes (PROs) which will be collected until 30 days after last study therapy administration, except in case of death, loss to follow-up or withdrawal of consent. For details please refer to [Section 7.1.5](#).

4.1.4 Efficacy follow-up

Patients who discontinue treatment for reasons other than disease progression or withdrawal of consent for efficacy follow-up, will continue to be followed every 8 weeks \pm 1 week for efficacy (i.e., tumor assessments and PROs) during the first 18 months and every 12 weeks \pm 1 week until 36 months, then change to as clinically indicated until disease progression, death, withdrawal of consent, loss to follow-up, subject/guardian decision. All scans will be acquired and analyzed for primary endpoint locally and will be sent to the Contract Research Organization (CRO) designated by Novartis for central imaging interpretation. If a patient starts a new antineoplastic treatment without withdrawing consent, the patient will continue to be followed for efficacy according to above specified protocol schedule until disease progression, death, withdrawal of consent, loss to follow-up, or subject/guardian decision. For further details please refer to [Table 7-1](#) and [Section 7.1.6](#).

4.1.5 Survival follow-up

All patients will be followed for survival once they discontinue study treatment and tumor evaluations until the final number of OS events have been reached or the study is stopped for other reasons. Survival follow-up will be done every 12 weeks \pm 1 week or earlier if a survival update is required to meet safety or regulatory needs. Survival information can be obtained by

clinical visits or telephone calls ([Section 7.1.8](#)) until death, the patient is lost to follow-up, or the patient withdraws consent for survival follow-up.

During the survival follow-up, in addition, subsequent [REDACTED]

[REDACTED] will be collected along with the [REDACTED]

[REDACTED] on subsequent therapies to assess [REDACTED]

4.2 Timing of interim analyses and design adaptations

Interim analyses for both the primary endpoint (PFS) and key secondary endpoint (OS) are planned for this study, in the *PIK3CA* mutant cohort. Interim analyses for the secondary endpoint, OS, in the *PIK3CA* non-mutant cohort are also planned.

An interim analysis that allows the cohort to stop for futility (non-binding) is planned after approximately 40% PFS events in the *PIK3CA* mutant cohort have been documented per local assessments. Another interim analysis that allows the cohort to stop for superior efficacy is planned after all patients in the *PIK3CA* mutant cohort have been randomized and approximately 75% PFS events have been documented, as per local assessments.

If PFS is statistically significant in either cohort, interim analyses for OS in that cohort will also be conducted. The interim analyses for OS will allow early stopping of the study for evidence of overwhelming efficacy of the alpelisib combination treatment compared to placebo. A maximum of three analyses are planned for OS in each cohort as detailed in [Section 10.5.1](#) and [Section 10.7](#).

4.3 Definition of end of the study

The end of the study for a given patient is defined as when the patient permanently discontinues study treatment with alpelisib + fulvestrant or placebo + fulvestrant and all the end of trial procedures are completed. The end of the overall study is defined as the time point when data collection will stop in both cohorts and the final analysis of the study will occur.

The primary analysis will occur when approximately the required number of PFS events is reached (refer to [Section 10.8](#)). The primary clinical study report (CSR) will be produced once the required number of PFS events is reached.

If the enrollment in the *PIK3CA* mutant cohort is stopped due to futility at the interim analysis or if the primary PFS analysis in the *PIK3CA* mutant cohort does not demonstrate a statistically significant treatment effect, then all subjects in each cohort will be followed for safety until 30 days post last dose and data collection will stop after all patients have discontinued study treatment and completed the safety follow-up period.

In the *PIK3CA* mutant cohort, if the primary endpoint of PFS is statistically significant the study will remain open, then patients still being followed, including patients in the *PIK3CA* non-mutant cohort, continue as per the schedule of assessments.

The study will end once the final OS analysis in the *PIK3CA* mutant cohort is performed approximately when the required number of deaths is observed or when statistical significance is reached for OS analysis (see [Section 10](#)) and the final analysis of study data is conducted. All available data from all patients in each cohort up to this cut-off date will be analyzed.

Patients continuing to derive benefit from study treatment in the opinion of the investigator at the end of the study will be able to continue receiving trial therapy on an individual basis (e.g. separate protocol or Novartis providing study treatment to the investigator as per local regulations).

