10.5.2.2 OS in patients with *PIK3CA* non-mutant status measured in tissue

OS analyses will be performed only if the secondary efficacy endpoint, PFS, in this cohort meets the PoC criteria given in [Section 10.5.2.1](#) and is statistically significant. A hierarchical testing procedure will be adopted. Assuming proportional hazards model for OS, the following statistical hypotheses will be tested at the one-sided 0.5% level of significance:

$$H_{01}: \theta_1 \geq 0 \text{ vs. } H_{a1}: \theta_1 < 0$$

where θ_1 is the log-hazard ratio (alpelisib + fulvestrant treatment arm vs. placebo+fulvestrant treatment arm) of OS.

The analysis for OS will be based on the FAS population according to the treatment arm patients were randomized to and the strata they were assigned to at randomization.

The final OS analysis will not be performed at the time point of the final PFS analysis in the *PIK3CA* non-mutant cohort, but after additional follow-up. Therefore, a three-look group sequential design is considered for OS.

If PFS in the non-mutant cohort meets the PoC criteria and is statistically significant at a one-sided 0.5% level of significance, OS will be hierarchically tested in the following way:

- The first timepoint for OS analysis will be at the time of the final analysis for PFS (provided PFS is statistically significant) when approximately 29% of the expected deaths are observed, at which point approximately 36 deaths in the *PIK3CA* non-mutant cohort have been recorded (after approximately 18 months from the first patient to be randomized in this cohort).

- If OS is not statistically significant at the first interim analysis, the 2nd OS analysis will be planned after approximately 87% of the expected deaths are observed, at which point approximately 109 deaths are expected to have been recorded in the clinical database.
- If OS is not statistically significant at the second interim analysis, a final analysis is planned after approximately 125 deaths are expected to have been recorded in the clinical database.
- If PFS is not statistically significant, then OS will not be tested.

OS will be estimated using the Kaplan-Meier method. The median OS along with 95% confidence intervals will be presented by treatment arm. Stratified Cox regression will be used to estimate the HR of OS, along with 95% confidence interval.

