* Probabilities are reported as if OS was tested alone, regardless the testing strategy with PFS. The true probabilities should take into account the probability of PFS at each look. Simulated probabilities shown based on the alpha allocated for testing (p=0.02).

At the time of final PFS analysis in this cohort, both PFS and interim OS analysis will be performed by the Sponsor's clinical team. Investigators and patients will remain blinded to study treatment and all patients will continue to be followed for OS until the final OS analysis (or earlier if OS reaches statistical significance at any of the interim analyses).

10.7.3 Secondary endpoint: Overall survival in the *PIK3CA* non-mutant cohort:

OS will be compared between the two treatment groups, provided PFS is statistically significant favouring alpelisib, in the *PIK3CA* non-mutant cohort. A hierarchical testing procedure will be adopted in this study and the OS analyses will be performed only if PFS is statistically significant. A maximum of three analyses are planned for OS:

- at the time of the final analysis for PFS (provided PFS is statistically significant) when approximately 29% of the expected deaths are observed, at which point approximately 36 deaths in the *PIK3CA* non-mutant cohort have been recorded (after approximately 18 months from the first patient to be randomized in this cohort);
- at the time when approximately 87% of the expected deaths are observed, at which point approximately 109 deaths in the *PIK3CA* non-mutant cohort have been recorded (after approximately 45 months from the first patient to be randomized in this cohort);

- a final analysis for OS when approximately 125 deaths in the *PIK3CA* non-mutant cohort have been recorded (approximately 54 months from date of first patient to be randomized in this cohort).

An α -spending function according to Lan-DeMets (O'Brien-Fleming will be used to maintain the overall type I error probability ([Lan and DeMets 1983](#)). The exact nominal p-values that will need to be observed to declare statistical significance at the time of these analyses for OS will depend on the number of OS events that have been observed at the time of these analyses and the α for OS already spent at the time of earlier analyses.

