Given the hierarchical testing strategy of PFS and OS, the design concerning OS analyses will have the following characteristics based on simulations in East 6.3. The probabilities shown in [Table 10-3](#) are conditional probabilities (conditional on PFS being statistically significant) not marginal probabilities.

Table 10-3 Simulated probabilities to stop for efficacy at 1st interim, 2nd interim, or final OS analysis in the *PIK3CA* non-mutant cohort

Scenario	Look	# deaths	Simulated cumulative probabilities (%) [*]	Simulated incremental probabilities (%) [*]
			Stop for efficacy	Stop for efficacy
Under H0 (HR.=1)	1st Interim	36	<0.001	<0.001
	2nd Interim	109	0.31	0.31
	Final OS	125	0.59	0.28
Under Ha (HR.=0.67)	1st Interim	36	0.001	0.001
	2nd Interim	109	24.59	24.58
	Final OS	125	36.74	12.15

Note: Simulations are performed in East 6.3 with number of simulations = 10,000 and randomization seed =60030. 1st Interim analysis will be conducted at the time of final analysis for PFS

* Probabilities are reported as if OS was tested alone, regardless the testing strategy with PFS. The true probabilities should take into account the probability of PFS at each look. Simulated probabilities shown based on the alpha allocated for testing ($p=0.005$).

At the time of final PFS analysis in this cohort, both PFS and interim OS analysis will be performed by the independent statistical group for the DMC. The Novartis Clinical team will remain blinded to study treatment allocations up until such point the *PIK3CA* mutant cohort can be unblinded. Investigators and patients will remain blinded to study treatment and all patients will continue to be followed for OS until the final OS analysis (or earlier if OS reaches statistical significance at any of the interim analyses).

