4. During the planned second OS interim analysis, test OS at $\delta_{mut}(t_{OS(s4mut)})$. If the OS efficacy boundary $v_{mut}(t_{PFS(s4mut)})$ is crossed then no more testing. If not then go to step 5.
5. During the planned final OS analysis, test OS at $\delta_{mut}(t_{OS(s5mut)})$. The study will be stopped at this step regardless of the outcome.

PIK3CA Non-mutant Cohort

- Let H_0 denote the null hypotheses for testing OS in the PIK3CA non-mutant cohort.
- Let $\delta_{\text{nonmut}}(t)$ denote the alpha-spending function for OS.
- Let $s_1 < s_2 < s_3$ denote the time points for:
 - Planned final analysis of PFS when targeted number of PFS events is expected to be observed (first OS interim analysis)
 - Planned second interim analysis of OS.
 - Planned final analysis of OS
- Let $t_{OS(s_1)}$, $t_{OS(s_2)}$, $t_{OS(s_3)}$ represent information fractions for OS at time points s_1 , s_2 , s_3 respectively.
- $v_{\text{nonmut}}(t_k)$ are the efficacy stopping boundaries for OS, at information fraction t_k .

Using the following testing strategy, the overall type-I error rate can be controlled:

- During the final PFS analysis, test PFS at 0.005:
 - If the PFS efficacy boundary is crossed then test OS at $\delta_{\text{nonmut}}(t_{OS(s_1)})$.
 - If the OS efficacy boundary $v_{\text{nonmut}}(t_{OS(s_1)})$ is also crossed then no more testing for OS.
 - If the PFS efficacy boundary is crossed but $v_{\text{nonmut}}(t_{OS(s_1)})$ is not crossed then we will continue to test OS as planned (go to step 2).
- During the second OS interim analysis, test OS at $\delta_{\text{nonmut}}(t_{OS(s_2)})$. If the OS efficacy boundary $v_{\text{nonmut}}(t_{OS(s_2)})$ is crossed then no more testing. If not then go to step 3.
- During the planned final OS analysis, test OS at $\delta_{\text{nonmut}}(t_{OS(s_3)})$. The study will be stopped at this step regardless of the outcome.

4.6 Statistical methodology and operating characteristics – PFS futility criteria in the PIK3CA mutant cohort

At the time of the futility analysis, the cohort may be stopped for futility if one or both of the following criteria are met:

- The observed (i.e. nominal) p-value > 0.128
- Conditional Probability ($HR_{\text{final}} \leq 0.6 | HR_{\text{interim}}$) < 0.20

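### Protocol 4.3 ends follow-up in both cohorts if the mutant cohort fails; this contradicts the separately gated non-mutant OS test and would cut off its second and final looks

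*Protocol*

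**What the plan says.** **The stopping rule.** Protocol 4.3 has two triggers, both in the mutant cohort: a futility stop at its interim, or a primary PFS analysis that is not significant. In either case "then all subjects in each cohort will be followed for safety until 30 days post last dose". Collection of data then ends once every patient is off treatment and past that safety period. No exception is made for a positive non-mutant cohort. The next paragraph of 4.3 keeps non-mutant patients on the assessment schedule when mutant PFS is significant. The study as a whole then ends with the mutant cohort's OS analysis.

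**The testing rule.** The other sections tie non-mutant OS to that cohort alone:

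- Protocol 4.2: "If PFS is statistically significant in either cohort, interim analyses for OS in that cohort will also be conducted".
- Protocol 10.5.2.2: "OS analyses will be performed only if the secondary efficacy endpoint, PFS, in this cohort meets the PoC criteria" and is significant. The three looks are then introduced by "If PFS in the non-mutant cohort meets the PoC criteria and is statistically significant at a one-sided 0.5% level of significance".
- Protocol 10.7.3: after the non-mutant PFS analysis, "all patients will continue to be followed for OS until the final OS analysis", or until OS is significant earlier.
- SAP 3.12.3 and the non-mutant steps in SAP 4.5.4: the same gate, with no condition on the mutant cohort.

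Protocol 10.4.2 gives the non-mutant cohort its own one-sided 0.5% by a Bonferroni split. On futility, Protocol 4.2 and 10.7.1 speak of stopping the cohort, whereas SAP 4.5.4 step 1 for the mutant cohort speaks of stopping the study.

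**The concern.** A pre-specified hypothesis with its own alpha is promised survival follow-up in one set of sections and denied it in another. The denial depends on data from different patients. A team that followed 4.3 literally would stop collecting survival data in a non-mutant cohort that had just met its proof-of-concept criteria and its formal PFS test. The 36.1% OS power in Protocol 10.9.1 could then not be delivered.

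Protocol 4.1.5 does not settle the matter, because it lets survival follow-up end when the study is stopped for other reasons. Nor does 4.4, which only reserves the sponsor's general right to terminate.

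**Working it through.** **1. Reproduce the stated power.** Inputs from Protocol 10.9.1 and 10.7.3: 125 deaths, HR 0.67, 1:1 allocation, one-sided 0.005, looks at 36, 109 and 125 deaths, Lan-DeMets O'Brien-Fleming spending.

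- Fixed design: |ln 0.67| × √125 / 2 − 2.576 = 2.239 − 2.576 = −0.337, so power is 36.8%.
- Three looks, spending function from SAP 4.5.1, with information fractions 0.288, 0.872 and 1:

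| Look | Deaths | Planned month | Cumulative alpha | Z boundary | Cumulative power | Table 10-3 |
|---|---|---|---|---|---|---|
| 1 | 36 | 18 | 0.00000017 | 5.10 | 0.005% | 0.001% |
| 2 | 109 | 45 | 0.00265 | 2.79 | 24.3% | 24.59% |
| 3 | 125 | 54 | 0.00500 | 2.63 | 36.1% | 36.74% |

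The stated 36.1% is reproduced.

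**2. Place the looks against the trigger.** The mutant decisions that can trigger 4.3 fall at about month 19 (futility, Protocol 10.7.1) and month 32 (final PFS, Protocol 10.8). The month-25 look is for efficacy only. I take the two cohorts' clocks as starting together. Look 1 at month 18 precedes both triggers; looks 2 and 3 follow both.

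**3. Deaths available.** Exponential survival with medians 30 and 44.8 months (Protocol 10.9), 7, 21 then 35 non-mutant patients per month to 220 (SAP 3.14), and 5% dropout. I assume the dropout is spread evenly over about 47 months.

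| Month | 18 | 19 | 32 | 45 | 54 |
|---|---|---|---|---|---|
| Modelled deaths | 35 | 39 | 78 | 107 | 124 |
| Plan | 36 | – | – | 109 | 125 |

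The model tracks the plan. At the triggers about 39 or 78 deaths exist, so look 2 needs about 70 or 31 more. Under 4.3 only deaths on treatment or within 30 days would still be recorded. I would not expect these to fill the gap, since treatment ends at progression.

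**4. Could an unplanned look rescue the test?** At about 78 deaths, the same spending function gives 5% to 6% power. If the whole 0.5% were spent there, |ln 0.67| × √78 / 2 − 2.576 = −0.81, or about 21%. The non-mutant steps in SAP 4.5.4 provide for neither.

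**5. How often the branch is reached at HR 0.6 in both cohorts.**

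- Non-mutant PFS positive: 0.491 × 0.983 = 0.483 (Protocol 14.6.2.2.1, SAP Table 4-2).
- Mutant failure, futility always acted on: 1 − 0.8395 = 0.1605 (Table 10-1), of which 0.1531 is the futility stop.
- Mutant failure, futility never acted on: |ln 0.6| × √243 / 2 − 2.054 = 1.93, so power is 97.3% and failure 0.027.
- Joint, assuming independence: 0.027 × 0.483 = 1.3%, up to 0.1605 × 0.483 = 7.7%.

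**The case against.** **The common stop may be deliberate.** Section 4.3 says each cohort, its next paragraph deals with the non-mutant cohort by name, Amendment 1 revised 4.3 for the change to proof of concept, and SAP 4.5.4 step 1 also stops the study. Closing a secondary OS test with 36.1% power is a sponsor's choice and does not inflate type I error. This stands as a possible intention. It does not remove the contradiction: the gate is then missing from every section that describes the test.

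**The branch is closed.** The rationale for Amendment 5 says that the study met its primary endpoint. This stands in full. A reader might infer that sites would now stop survival calls; they would not, because the failure clause can no longer be triggered.

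**The futility rule is non-binding, and the DMC also receives the non-mutant PFS result.** It could weigh a positive result before recommending a stop. This stands, and it is why 7.7% is only the upper end of a range.

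**Section 4.3 does not name survival follow-up**, and data collection continues until all patients are off treatment. This is correct. Its loss is nevertheless the plain reading of safety-only follow-up, and patients still on treatment cannot be expected to supply the missing deaths.

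**Cohort-specific follow-up could unblind mutation status.** Sites are kept blinded to it (Protocol 2.2, 4.1.2). This stands and shapes the fix.

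**Conclusion.** The contradiction is real. If 4.3 is followed after a mutant failure, a PFS-positive non-mutant cohort keeps OS look 1 only, with a crossing probability of 0.001% to 0.005% against a planned 36.1%. The chance of reaching that situation is about 1.3% to 7.7%, assuming HR 0.6 in both cohorts, independence, and the plan's timelines.

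Two stronger readings are not supported:

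- A reader might infer that non-mutant OS could never be tested. The first look is planned before any mutant decision, so it can take place, although with almost no alpha.
- A reader might infer that the 102-event proof-of-concept PFS analysis is also at risk. Table 10-5 puts the 102nd event at 18.0 months for HR 0.6 and 18.7 for HR 0.5, both before month 19. Only HR 0.4 (19.7) and HR 0.3 (21.0) fall later.

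With the primary endpoint met, this is a fault of design and internal consistency and has no remaining effect on conduct in that branch.

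**What to change.** **If the non-mutant test is meant to stand alone:**

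- In Protocol 4.3, keep survival follow-up for a cohort whose own PFS is significant (for the non-mutant cohort, PoC met and PFS significant) until that cohort's final OS analysis.
- Define the end of the study by the later of the cohorts still under test.
- In SAP 4.5.4 step 1, have the futility boundary stop the mutant cohort instead of the study.

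The cost is wording plus, in that branch only, 12-weekly survival contact for about 220 patients, which may be by telephone. Alpha and sample size do not change. The downside is that follow-up in one cohort only could disclose PIK3CA status to sites. Continuing survival calls in both cohorts avoids this, at the cost of contacting mutant patients too.

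**If the common stop was intended:** state the mutant-cohort gate in Protocol 4.2, 10.5.2.2 and 10.7.3 and in SAP 4.5.4, and describe the 36.1% power as conditional on mutant PFS success. This costs wording only.
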